4.3 ANALYSIS OF TREATMENT ARM COMPARABILITY

To ensure the comparability of the treatment arm, the randomization will be stratified by the availability of a previous MMF treatment (yes/no) and the presence/absence of IPAF as defined by MDT to ensure an equal distribution of patients.

These stratification factors will be included in the analysis of the primary endpoint as a sensitivity analysis. Please refer to the corresponding section 4.4.5 for further details.

Outputs for concordance between the stratification factors by eCRF and by IxRS will also be presented.

4.4 ANALYSIS OF STUDY CONDUCT

Unless otherwise specified, all analyses described in this section will be performed on the ITT population, presenting data by treatment arm.

4.4.1 Patient Disposition

An overview on patient disposition, showing number and percentages of patients enrolled, screened, failed screening, randomized, treated, completed or early discontinued the double-blind treatment period, patients entering the 12-month safety follow-up period and their current status (ongoing, completion, discontinued) in that period will be provided. For patients who have early discontinued the double-blind treatment period or the study, frequencies of reasons for early discontinuation will be provided. A listing with all the patient disposition data will be also presented.

The following definitions will be used:

 Patients randomized: All patients who have been randomized to receive either pirfenidone or placebo, i.e. have a randomization date.

Pirfenidone — F. Hoffmann-La Roche Ltd

- Patients randomized and not treated: all randomized patients who have not received at least one dose of the randomized treatment.
- Patients randomized and treated: all randomized patients who have received at least one dose of the randomized treatment.
- Patients randomized and treated with sufficient post-baseline efficacy data: all randomized patients who have received at least one dose of the randomized treatment and have at least one post-baseline assessment of FVC (mL).
- Completion of double-blind treatment period: eCRF question "Did the patient complete course of double-blind treatment?" is ticked "Yes" (eCRF form "Doubleblind treatment Completion/Early Discontinuation").
- Early discontinuation (non-completion) of double-blind treatment period: eCRF
 question "Did the patient complete course of double-blind treatment?" is ticked "No"
 (eCRF form "Double-blind treatment Completion/Early Discontinuation").
- Early discontinuation (non-completion) of study: eCRF question "Did the subject early discountinue from the study?" is ticked "Yes" (eCRF form "Study Completion/Early Discontinuation") for patients who discontinued double-blind treatment period.
- Status during the 12-month safety follow-up (entered, ongoing, completed).
 Completers are defined as those patients that have filled the study completion/discontinuation form. Otherwise, the patient is considered ongoing in the safety follow-up phase.
- Completion of study: eCRF question "Did the subject complete the study?" is ticked "Yes" (eCRF form "Study Completion/Early Discontinuation")
- Early discontinuation (non-completion) of study: eCRF question "Did the subject early discountinue from the study?" is ticked "Yes" (eCRF form "Study Completion/Early Discontinuation")

An overview on patients' enrolment will be provided based on the randomized subjects by country and center separately for the pirfenidone and placebo arm.

Kaplan-Meier (KM) plots for time to treatment discontinuation will be provided for all randomized patients and by randomized arm, based on the date subject completed or early discontinued from double-blind treatment period, as per eCRF. If the patient completed the treatment without treatment discontinuation, then it will be censored to the date of treatment completion.

In addition, KM plots for time to study discontinuation will be presented for all randomized patients by arm, based on the study discontinuation date. If the patient completed the study as planned per protocol, then the patient will be censored to the study completion date.

Pirfenidone — F. Hoffmann-La Roche Ltd

In addition, a consort diagram with some of the categories above will be presented.

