2.2.4 Safety Outcome Measures

The safety objective for this trial is to evaluate the safety of pirfenidone vs. placebo by investigating the following endpoints:

- Nature, frequency, severity, and timing of treatment-emergent adverse events
- Dose reductions and treatment interruptions
- Clinical laboratory test results
- 12-lead ECGs
- Withdrawals from trial treatment or trial discontinuations

All analyses with regard to the safety outcome measures will be performed from the date of first randomized treatment intake until 28 days after the last positive dose during the double-blind randomized treatment period.

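### The SAP's status rule for the 12-month safety follow-up counts patients who stop early or die as completers

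*SAP*

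**What the plan says.** SAP version 3.0, section 4.4.1 (Patient Disposition), describes status in the 12-month safety follow-up twice.

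- The opening paragraph commits the disposition overview to patients entering the follow-up and says that "their current status (ongoing, completion, discontinued) in that period will be provided".
- The list of definitions below it has a bullet beginning "Status during the 12-month safety follow-up (entered, ongoing, completed"). It then states: "Completers are defined as those patients that have filled the study completion/discontinuation form". The next sentence disposes of the rest: "Otherwise, the patient is considered ongoing in the safety follow-up phase".

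The neighbouring bullets work differently. Study completion and study early discontinuation are each taken from a Yes answer to a specific question, and both questions sit on the same combined completion/early-discontinuation eCRF form. Double-blind completion is likewise defined by a ticked Yes or No, on its own form.

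**The concern.** The follow-up bullet asks whether a form exists, not what was answered on it. Because the form serves both outcomes, its existence shows only that the patient is no longer in the study. An entrant who withdraws from open-label pirfenidone, or dies, therefore falls under completed, and the bullet offers no other category for a patient with a form.

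At stake is the reported completion rate for the open-label year. Section 4.7 reports adverse-event incidence for that year, and readers use the completion figure to judge how much of the planned follow-up lies behind it. A rate that cannot fall below 100% once all forms are in would mislead them.

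**Working it through.** The plan states no figure for follow-up completion, so there is none to reproduce. The check is of the rule's logic, followed by a short illustration.

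**1. Who has a form on file?**

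- Section 4.2.5 ends the follow-up at the study completion/discontinuation visit, so early stoppers reach this form as well as finishers.
- Section 4.6.3 says that death information is collected on the eCRF panel for study discontinuation. A patient who dies should therefore have discontinuation data on file.
- Section 4.2.6 sets the final cut-off after all patients have finished the follow-up, so nobody should still be ongoing by then.

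**2. How each rule classifies an entrant**

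| Entrant | Follow-up bullet | Opening paragraph's categories | Study-level rows |
|---|---|---|---|
| Finished the year | completed | completion | completed |
| Stopped early or died | completed | discontinued | early discontinuation |
| No form yet | ongoing | ongoing | neither |

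The second line is the fault. The bullet disagrees with its own opening paragraph and with the study-level rows. At the primary cut-off, the patients it calls completed would be a mixture of early leavers and genuine finishers.

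**3. Size at the final cut-off**

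Let E be the number of entrants, F the forms filed, and d the share who stop early or die.

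- Reported completion = F / E. If all forms are filed, F = E and this is 100%.
- True completion = 1 − d.
- Overstatement = 1 − (1 − d) = d; patients misclassified = E × d.

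The documents give neither E nor d, so both are assumed. For E = 200:

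| d (assumed) | Reported | True completers | Misclassified |
|---|---|---|---|
| 5% | 200 (100%) | 190 (95%) | 10 |
| 10% | 200 (100%) | 180 (90%) | 20 |
| 20% | 200 (100%) | 160 (80%) | 40 |
| 30% | 200 (100%) | 140 (70%) | 60 |
| 40% | 200 (100%) | 120 (60%) | 80 |

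For E from 150 to 250 over the same d, the number misclassified runs from 8 (150 × 0.05 = 7.5, rounded) to 100 (250 × 0.40).

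**4. Can the correct figure be recovered from the other summary rows?**

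Not by subtraction. The general study-level early-discontinuation row covers the whole study. Version 3.0 has a separate row for study discontinuation among patients who discontinued double-blind treatment. It no longer has version 2.0's row for patients who completed double-blind treatment, did not enter the follow-up and discontinued the study. Taking the first group out of the total therefore leaves non-entrants mixed with open-label leavers. Section 4.7 does not define follow-up disposition, so the bullet in 4.4.1 is its only definition.

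**The case against.** The best defence is that the opening paragraph shows the intent: three states, with the bullet meant only to separate patients who have left the follow-up from those still in it at the primary cut-off. That is a plausible reading of intent. It does not rescue the bullet, which gives an explicit definition of completer that a programmer would have to override.

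The defence is stronger on consequences. A reader might draw four larger conclusions that the documents do not support.

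- *That early stopping is hidden.* It is not. Section 4.4.1 still provides study completion and discontinuation from the ticked answers, frequencies of reasons, a listing of all disposition data and a Kaplan-Meier plot of time to study discontinuation. Section 4.6.3 lists deaths with a flag for study period, and section 4.7 summarises open-label treatment duration.
- *That a stated safety endpoint is misreported.* Section 2.2.4 does list "Withdrawals from trial treatment or trial discontinuations", but it limits the safety outcome analyses to the period from first randomized intake until 28 days after the last double-blind dose. The open-label year lies outside that endpoint.
- *That long-term retention is an objective.* No objective or endpoint in the protocol or SAP concerns it.
- *That completion is overstated by some known amount.* No drop-out rate or number of entrants is given, so any percentage is an assumption restated.

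Nor do the documents show that the follow-up row and the study-level rows share one table, since no table shell is included. Version 2.0 carries the same wording, but it is superseded and is not a second instance in the current plan.

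**Conclusion.** The rule is wrong as written. In the follow-up status row, entrants who stop early or die are counted as completed. Once every entrant has a form, the row reports 100% completion and carries no information about drop-out. This contradicts the categories promised in the same section and the study-level definitions beside it.

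The 100% result rests on applying the bullet literally to patients who entered the follow-up, and on all forms being filed by the final cut-off. The overstatement equals the unknown early-stop rate; the 5% to 40% range is illustrative only.

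The reach is narrow: descriptive follow-up disposition, and any CONSORT box drawn from that category. No hypothesis test, efficacy estimate or double-blind safety endpoint changes, and the patient-level facts are reported correctly elsewhere. It merits correction because it would put a wrong number in the report, and because the remaining summary rows do not by themselves isolate open-label leavers.

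**What to change.** Replace the two sentences in the section 4.4.1 bullet with a rule restricted to patients who entered the follow-up:

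- **completed**: the form's study-completion question is ticked Yes;
- **discontinued**: the form's early-discontinuation question is ticked Yes, shown with the reason, including death;
- **ongoing**: no form filed.

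Change the bullet's category list to match the opening paragraph, and use the same three states in the disposition overview and the CONSORT diagram.

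The cost is a short text change and a small derivation change on existing eCRF fields, with no new data. Section 4.5.8 says the primary analysis was performed in March 2019, so any follow-up status output already produced under this rule would need to be rerun. The reported completion rate will fall to its true value.

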4.4.2 Major Protocol Deviations

Major protocol deviations and eligibility violations will be summarized by frequency tables and all patients with protocol deviations will be listed. Protocol deviations will be collected in the protocol deviation management system (PDMS), reviewed by the medical monitors. All deviations provided in that dataset will be considered as major protocol deviations.

4.4.3 Demographic and Baseline Characteristics

Baseline and disease characteristics such as demographics, medical history and tobacco use history will be summarized by descriptive statistics or frequency tables for each treatment arm.

Demographics

The following demographic characteristics will be summarized by treatment arm:

- Age (years): as entered in the eCRF at the screening visit.
- Age categories: <65, and ≥ 65.
- Age categories: <45, ≥45 to <65 years, ≥65 to <85 years, and ≥ 85 years.
- Gender: Male/Female.
- Race: White, American Indian or Alaska Native, Asian, Black or African American, Native Hawaiian or Other Pacific Islander, Unknown. In case that more than one race will be ticked, a concatenated variable, containing all races will be presented (e.g. Asian/White).
- Ethnicity: Hispanic or Latino, Not Hispanic or Latino, Not reported, Unknown.
- Weight (kg) at baseline
- Height (cm) at baseline
- BMI (kg/m2) at baseline. BMI will be calculated as: weight(kg) / (height(m))2
- Female reproductive status: childbearing potential without contraceptive protection, Childbearing potential with contraceptive protection, surgically sterilized, Postmenopausal, Pre-menarchal, Non childbearing potential.

Data on female reproductive status will be presented descriptively.

Demographic data will be also listed.

Pirfenidone — F. Hoffmann-La Roche Ltd

Medical History

Medical history will be coded using the Medical Dictionary for Regulatory Activities (MedDRA®), version 20.1 or higher and will be summarized presenting numbers and frequencies by primary System Organ Class (SOC) and Preferred Term (PT) by treatment arm. If patients have more than one disease within a SOC or PT they will be counted only once for the respective SOC or PT.

A listing with past and ongoing medical history data from the washout period will be presented.

Tobacco use history

The history of tobacco use will be summarized by treatment arm with the following characteristics:

- Tobacco use history (never, current, previous)
- Nicotine exposure (pack-years), smokers only

Numbers and percentages of patients will be provided for tobacco use history. Nicotine exposure will be summarized descriptively.

Diagnosis and time from uILD Diagnosis

Frequencies and percentages will be presented for the uILD category collected into the eCRF page MDT/Diagnosis (Eligibility).

The time in months since the original uILD diagnosis will be calculated as

Date of randomization – Date of ILD diagnosis and will be summarized descriptively by randomized treatment arm. The number and percentage of patients with a historical high-resolution computed tomography and with a historical surgical lung biopsy will also be presented.

Descriptive statistics of the time from most recent historical high-resolution computed tomography (months) and historical surgical lung biopsy will be presented. As above, the date of randomization will be used as reference date for calculation of duration.

Stratification Factors

The number and percentage of patients that fall into each of the four groups based on the two stratification factors: Concomitant MMF treatment (yes/no), and the presence/absence of IPAF as defined by the MDT will be presented by treatment arm.

Baseline Site Spirometry Test

The values recorded for the baseline assessments of the site spirometry tests were the following:

Pirfenidone — F. Hoffmann-La Roche Ltd

- Forced vital capacity (FVC) (L and % predicted)
- Forced expiratory volume in 1 second (FEV1) (L and % predicted)
- FEV1 (L) / FVC (L) ratio (1)
- Carbon monoxide diffusing capacity (DLco) (% predicted)

Descriptive statistics will be provided for these parameters separately for treatment arm.

Historical Spirometry Test

The number and percentage of patients who performed spirometry test (FVC, DLco, FEV1, and FEV1/FVC ratio) in the past will be provided. The most recent assessment before the Screening visit will be collected:

- Hemoglobin corrected DLco (mmol/min/kPa and %)
- DLco/Va (KCO) (mL/min/mmHg/L and % predicted)
- FVC (L and % predicted)
- FEV1 (L and % predicted)
- FEV1(L)/FVC(L) ratio (1)

These historical spirometry test parameters will be summarized using descriptive statistics by treatment arm. Both, absolute and percent predicted values will be presented. Frequencies and percentages will be presented for the high-resolution computed tomography and the surgical lung biopsy.

Baseline 6-minute walk distance (6MWD)

The 6MWD is used to evaluate the functional capacity of patients with lung disease. The 6MWD measures the distance a patient is able to walk quickly on a flat, hard surface in a period of 6 minutes.

The number and percentage of patients that

- Performed the 6-minute walking test (yes/no),
- Rested for at least 10 minutes (yes/no),
- Stopped the test before 6 minutes (yes/no),
- Required O2 (yes/no)

at the baseline visit will be summarized by randomized treatment group.

Pirfenidone — F. Hoffmann-La Roche Ltd

The values of the parameters recorded for the 6MWD test are:

- Vital signs (Heart rate (beats/min), systolic blood pressure (mmHg), diastolic pressure (mmHg)) (before the test, at the end of the test)
- Distance walked (m),
- Oxyhemoglobin saturation (SPO2) (before the test (at rest), at the end of the test),
- Oxygen (O2) requirements (L) for patients who received oxygen (at the end of the test)

will be summarized descriptively by treatment arm.

4.4.4 Previous and Concomitant Medication

Previous and concomitant medications will be presented based on the safety population. Post medications administrated during the safety follow-up period will be presented based on the safety follow-up population.

Previous and concomitant medications are non-study medications. Concomitant therapy includes any medication used by a patient from the washout period until 28 days after the last dose of trial treatment. The previous and concomitant medication will be coded using the Genentech (GNE) drug dictionary. This is a proprietary Roche Dictionary which is used to code concomitant medications in the Trial Management System (TMS) coding tool. The Standardized Medication Name (CMDECOD), which is the medication generic or combination generic as defined by the Drug Thesaurus (proprietary Genentech/Roche dictionary), and the Medication Class (CMCLAS), which is the primary medication class as defined by the Drug Thersaurus, will be used for the analyses.

Therapies will be classified as previous or concomitant as follows:

Previous: If the medication start date is prior to start of double-blind treatment,

Concomitant: If medication is taken at any time between the start of double-blind treatment and 28 days after last positive dose of randomized treatment.

Post (safety follow-up): If the medication is taken more than 28 days after the last positive dose of randomized treatment.

The number and frequency of previous and concomitant medications taken by patients in the two treatment arms will be presented by Medication Class and Standardized Medication Name. If patients receive more than one drug within a Medication Class or Standardized Medication Name they will be counted only once for the respective Medication Class or Standardized Medication Name.

Pirfenidone — F. Hoffmann-La Roche Ltd

A separated table will be presented for post medications during the safety follow-up period.

All medications will be listed identifying the previous/concomitant and post medications.

The missing imputation rules for the medication dates are described under Section 4.9..

4.4.5 Daily Spirometry (Handheld Device)

A handheld spirometry device will be used by the patient to measure daily FVC at home. Confirmatory site (trial center) based FVC measurements will be conducted every 4 weeks. The following blow categories will be collected:

| Quality description | Acceptable text |
|---------------------|-----------------|
| Accepted | YES |
| Rejected | NO |
| Borderline Accepted | BOR |

Only accepted blows will be considered for the analysis. If one patient has more than one measurement per day, the last measurement will be taken.

FVC (mL) will be measured daily with a handheld device.

After primary analysis of study data it was detected that FVC values from home spirometry were impacted by high variability and implausible values were accepted by the system. In order to evaluate the issue a re-read of home spirometry data will be performed and the new dataset with modified flagging of acceptable values will be analyzed in the same way as described below for the primary endpoint, see also 4.5.2.

4.4.6 Compliance

With respect to the home-based daily measurements compliance of patients will be investigated. It will be analyzed if gaps of measurements occur over time. A gap is thereby defined as 7 or more than 7 consecutive days of missing measurements. A summary table displaying number of patients with gaps in daily measurements, number of gaps and duration of gaps will be provided by treatment arm for data from handheld spirometer.

4.5 EFFICACY ANALYSIS

The primary and secondary efficacy analyses will include all patients in ITT population, with patients grouped according to their assigned treatment.

Pirfenidone — F. Hoffmann-La Roche Ltd

The primary analysis of the primary efficacy endpoint of this study is planned to be performed when the last patient reached the date of the last follow-up visit after end of the double-blind treatment period (clinical cut-off date).

4.5.1 Primary Efficacy Endpoints

The primary efficacy objective for this trial is to evaluate the efficacy of pirfenidone vs. placebo on lung function parameters on the basis of rate of decline in FVC in mL measured by handheld spirometer over the 24-week double-blind treatment period.

The primary analysis will be based on the ITT population. Patients who discontinue treatment prematurely will be analyzed based on the available data. No imputation method will be applied for the primary endpoint.

The primary analysis of the primary endpoint will compare the mean FVC decline in each treatment arm using a student's t-test with a two-sided significance level α =0.05. The mean FVC decline for each treatment arm will be calculated using the estimated FVC decline for each individual patient. The estimated FVC decline for individual patients will be obtained by applying a linear regression model to all data points collected during the 24-week double-blind treatment period:

$$X_{it} = \alpha_i + \beta_i D_{it} + u_{it}$$

where

 X_{it} = the FVC measurements (mL) of patient i on day t, with i=1,...,N and t=1,...,T, being N the total number of patients randomized and T the total number of days with assessment.

 D_{i*} = study day t of patient i

 α_i, β_i = intercept and slope of the individual linear regression of patient i

The time-adjusted decline for patient i is then obtained by estimating the patients' individual difference in predicted values between baseline and week 24 from the linear regression.

In a further step, the time-adjusted mean FVC decline is estimated by calculating the mean over all individual time-adjusted declines of all patients by treatment arm.

A summary table displaying the mean FVC decline together with two-sided 95% confidence intervals based on percentiles of the t-distribution will be provided by treatment arm. The mean FVC decline in each treatment arm will be compared using a student's t-test with a two-sided significance level α =0.05. Additionally, a two sample Wilcoxon test will be used for treatment comparison. Results of this test are of descriptive nature only.

The same analyses will be done by restricting the FVC decline values:

- Including patients with at least 3 site spirometry measurements Pirfenidone — F. Hoffmann-La Roche Ltd

- excluding patients with a predicted FVC decline below -1000 mL
- or above 1000 mL
- excluding values with a difference +/-50% from corresponding baseline site spirometry

Mean FVC declines and results from Student's t-test by subgroups (for definition see 4.5.6) will be displayed in a forest plot.

As a sensitivity analysis to the primary analysis, the time-adjusted mean FVC decline will be estimated by a repeated measures mixed model with patient effects fitted as random and day of measurement and treatment fitted as fixed effects. Please refer to Section 4.5.6 for further details.

A detailed description of SAS code to be used for the repeated measures mixed model is provided together with the respective table shell.

